6.2 Study population

6.2.1 Inclusion criteria

- a) ≥ 18 years of age
- b) Trauma resulting in grade III or higher splenic injury on contrast-enhanced CT as defined by the AAST guidelines
- c) Splenic injury to be treated by non-operative management as decided by attending trauma surgeon and interventional radiologist
- d) Patient will undergo proximal splenic artery embolization as decided by the attending interventional radiologist

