6.3 Recruitment

An attending trauma surgeon will evaluate all trauma patients. Patients with a confirmed grade III or higher splenic injury on contrast-enhanced CT will be considered for entry into the study. Typically, hemodynamically unstable patients or stable patients with additional injuries that would require abdominal surgery are managed operatively while all others are candidates for non-operative management. The decision to proceed with

splenic artery embolization will be made by an attending interventional radiologist in conjunction with the attending trauma surgeon.

Clinicians will be assisted by research associates (RAs) from the Alabama Resuscitation Center (ARC), who are available 24 hours per day, and will screen all patients with grade III (and higher) splenic injuries for entry into the study. The RAs will discuss the protocol with the patient and/or their representative, and notify the trauma team if they are prepared to participate. The RA will notify both the attending trauma surgeon, and the interventional radiologist, that the patient is potentially eligible for the study. Once the attending interventional radiologist deems the patient an appropriate candidate for SAE, the interventional radiology team will screen the patient for eligibility. Once deemed eligible, informed consent for the procedure *and* the study will be obtained by the interventional radiology service from either the patient or their legally-authorized representative. If the patient is unable to consent for themselves *and* the legally-authorized is not physically present, the patient will be considered excluded from the study. All study and consent discussions will take place in a private room, away from other patients, so that conversations cannot be overheard and potential subjects cannot be publicly identified.

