6.4 Randomization

[figure not shown]
After meeting the above criteria and obtaining informed consent, the patient will be randomized to either the coil arm or arm. Randomization will occur by sealed numbered envelopes. The sealed envelopes will be located in the Interventional Radiology Reading Room in the Heart and Vascular Center (6th floor, North Pavilion). This is a secure area requiring badge access at all times.

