9. DATA COLLECTION

Data is abstracted into an electronic case report form (eCRF) by study staff. The eCRF uses the Research Electronic Data Capture (REDCap) system, a secure research database developed by the NIH. A full list of variables to be collected is shown below. Data logic checks are used to minimize data entry errors.

The following admission parameters will be collected:

- a) Source of patient (transferred from another facility or from the scene of injury?)
- b) Mechanism of injury
- c) Date and time of arrival
- d) Vital signs (temperature, heart rate, blood pressure, respiratory rate)
- e) Use of vasopressors at time of arrival
- f) Intubated at time of arrival
- g) Glasgow Coma Scale (GCS)
- h) Injury Severity Scale (ISS)
- i) Undergoing massive transfusion protocol?

The following blood tests, which are all measured routinely as part of the clinical assessment of trauma patients, are collected, as soon as possible upon arrival:

- a) Arterial blood gas
- b) Hemoglobin and hematocrit
- c) Platelet count
- d) Coagulation parameters including prothrombin time (PT), international normalized ratio (INR), activated partial thromboplastin time (APTT), and Anti-Xa
- e) Thromboelastograph (TEG) or thromboelastogram (ROTEM)

The following data points will be extracted from the initial CT report (emergent):

- a) Phase of enhancement
- b) Splenic injury grade according to AAST guidelines

- c) Signs of accompanying vascular injury such as pseudoaneurysm, extravasation, arterio-venous fistula, or hemoperitoneum
- d) Presence or absence of other intra-abdominal or extra-abdominal trauma

The following data points will be collected from the embolization procedure:

- a) Duration
- b) Radiation dose
- c) Contrast type and volume
- d) Splenic artery diameter
- e) Presence of pseudoaneurysm, arterio-venous fistula, or contrast extravasation on angiography
- f) Embolization material
 - a. Primary (coils vs. vascular plugs)
 - b. Secondary (beads, coils, vascular plugs, foam, other)
- g) Technical success
- h) Intra-procedural complications (non-target embolization, migration of the coil or vascular plug, ineffective treatment requiring splenectomy, vessel rupture, injury at the access site, and splenic infarction/abscess)

The following data points will be collected from the over-read of the CT (non-emergent):

- a) Phase of enhancement
- b) Splenic injury grade according to AAST guidelines

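### The randomization envelopes are kept inside the interventional radiology service, which also screens, consents and treats, so the stated custody does not protect allocation concealment

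*Combined protocol and SAP*

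**What the plan says.** **Allocation (section 6.4).** "Randomization will occur by sealed numbered envelopes". On storage: "The sealed envelopes will be located in the Interventional Radiology Reading Room in the Heart and Vascular Center". On protection: "This is a secure area requiring badge access at all times". On timing: "After meeting the above criteria and obtaining informed consent, the patient will be randomized".

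**Entry and treatment.**
- Section 6.2.1(c): "Splenic injury to be treated by non-operative management as decided by attending trauma surgeon and interventional radiologist".
- Section 6.2.1(d): "Patient will undergo proximal splenic artery embolization as decided by the attending interventional radiologist". Section 6.3 adds that this decision is taken together with the attending trauma surgeon.
- Section 6.3: research associates, available around the clock, first screen all patients with grade III or higher injury and alert both the surgeon and IR. Then "the interventional radiology team will screen the patient for eligibility", and the IR service obtains consent for both the procedure and the study.
- Section 7.3: an attending interventional radiologist performs every embolization.

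**Device preference and anatomy.** Section 3 says that the embolic agent is currently chosen mainly on the operator's experience and preference, and that the stiffer plug system may be hard to use in tortuous arteries. Section 7.2 adds that the largest plug of one type may be too small for some arteries.

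The text does not say how the sequence is generated, whether it is blocked, or who prepares, holds or opens the envelopes. It is also silent on whether they are opaque, tamper-evident, opened in strict order or logged.

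**The concern.** Concealment works when those who can influence whether a patient enters cannot know, or find out, which arm comes next. Here the place of storage belongs to the service that takes the last entry steps and then uses the device. A badge-controlled door keeps outsiders away from the envelopes but does not keep IR staff away.

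There is a reason why foreknowledge could matter in this trial. A patient whose anatomy looks unfavourable for a plug could be left out, or entered later, when a plug is next. Under section 7.3, failure to reach the mid-splenic artery is recorded as a technical failure, so the feature that might prompt selection also drives a listed outcome. Technical success, use of a secondary embolic, radiation dose and cost would all be exposed. Those comparisons are meant to choose endpoints for the larger trial.

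**Working it through.** **1. The plan's own figure.** Section 10 expects about 100 splenic artery embolizations in 12 months and counts 50% as success: 0.50 × 100 = 50, or 25 per arm. This reproduces and is not disputed. It is a recruitment target, not a power calculation. It also means that about half of the candidates may stay outside the trial, so a selectively withheld patient need not stand out.

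**2. Custody set beside discretion.**

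| Step | Who | Section |
|---|---|---|
| First screen | Research associates | 6.3 |
| Non-operative management | Trauma surgeon and IR | 6.2.1(c) |
| Embolization decision | IR attending, with trauma surgeon | 6.2.1(d), 6.3 |
| Final eligibility screen | IR team | 6.3 |
| Study consent | IR service | 6.3 |
| Storage of envelopes | IR Reading Room | 6.4 |
| Opening of envelopes | Not stated | 6.4 |
| Procedure | IR attending | 7.3 |

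That IR staff hold badges to their own reading room is an inference, though a safe one.

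**3. Illustrations.** The documents give no figure for steering, so everything below rests on assumptions.

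*Effect of one patient.* 1/25 = 4 percentage points. Three patients make 3/25 = 12 points, for example 22/25 = 88% against 25/25 = 100%. This needs each diverted patient to have failed and each replacement to succeed. The 88% is not in the documents.

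*Predictability without touching an envelope.* Operators see each device used. With 1:1 blocks of known size 2m (assumed), the expected share of allocations that follow with certainty from past ones is 1/(m+1):

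| Block size | Share known |
|---|---|
| 2 | 1/2 = 50% |
| 4 | 1/3 = 33% |
| 6 | 1/4 = 25% |
| 8 | 1/5 = 20% |
| One list of 50 | 1/26 = 3.8% |

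*Imbalance.* Suppose a share p = 0.30 of candidates has difficult anatomy, and a fraction f of these is withheld whenever a plug is next. The plug arm's share is p(1 − f)/(1 − pf), against 0.30 in the coil arm:
- f = 0.25: 0.225/0.925 = 24%
- f = 0.50: 0.150/0.850 = 18%
- f = 1.00: 0%

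*False-positive rate.* With 25 per arm, two-sided 0.05 (sidedness assumed), no true device effect and a selection-induced shift of d SD, the normal approximation is Φ(d/√(2/25) − 1.96) + Φ(−d/√(2/25) − 1.96):

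| d | Rate |
|---|---|
| 0 | 5% |
| 0.2 | 11% |
| 0.3 | 19% |
| 0.5 | 42% |
| 0.8 | 81% |

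*Linking the last two.* If difficult anatomy shifts a continuous outcome by 1 SD (assumed), then d equals the difference in shares:
- f = 0.25: 0.300 − 0.243 = 0.057, rate about 5.5%
- f = 0.50: 0.300 − 0.176 = 0.124, rate about 7.2%
- f = 1.00: 0.300, rate about 19%

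A shift of 0.5 SD would need complete withholding and an anatomy effect of 0.5/0.30 = 1.7 SD. The lower rows of the table are therefore extreme.

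**4. Enrolment fraction.** Against the roughly 100 embolizations of section 10, each withheld patient who is still embolized takes 1/100 = 1 point off.

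**The case against.** The strongest reply is that section 6.4 has real safeguards: the envelopes are sealed and numbered, the room is controlled, and allocation follows eligibility and consent. People outside IR also take part. Research associates meet candidates before the IR screen, and the trauma surgeon shares two decisions, so a withheld candidate would be known to others. All of this stands. It lowers the risk but does not remove the overlap between custody and the last entry steps.

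The anatomical route is also partly inferred. Section 9 lists neither tortuosity nor arterial diameter among the CT items, and section 7.3 has diameter measured during the procedure, after randomization. Operators may still judge anatomy from the CT required for entry, but the documents do not say so.

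A reader might infer more than the text supports:
- **That IR can learn the next arm, or opens the envelopes.** No one is named as opener. Whether an arm could be read early depends on opacity, tamper evidence and order of opening, which are not described. The figure in section 6.4 was not available for this review; if it names a custodian outside IR, the point changes.
- **That the trial already has a concealed allocation system.** Section 9 says only "The eCRF uses the Research Electronic Data Capture (REDCap) system"; a randomization function is not mentioned.
- **That a 12-point bias is to be expected.** It restates an assumed three diverted patients. Even 22/25 against 25/25 gives a two-sided Fisher p of 2 × 2,300/19,600 = 0.23.
- **That the feasibility result would be flattered.** Against the section 10 denominator, withholding patients lowers the fraction and so works against declaring success. Switching a patient between arms leaves it unchanged.

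**Conclusion.** The concern holds as an unprevented risk of selection bias. It rests on the custody that section 6.4 states, not merely on detail left out: the envelopes are in the operators' own room, and nothing described separates them from the service that completes entry. The missing detail on envelopes and sequence means that no other safeguard can be relied on.

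The main exposure is the Aim 2 comparisons; Objective 1a is a lesser one. No size can be derived from the documents. Up to 4 points per diverted patient is the scale for a proportion. For a continuous outcome, the false-positive rate runs from about 5.5% to 19% if 25% to 100% of difficult cases are withheld before a plug, with 30% difficult cases and a 1 SD anatomy effect, all assumed. The arrangement should be changed because the remedy is cheap, not because bias has been shown.

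**What to change.** Move allocation out of IR's custody, by either route:

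1. **Central release.** Allocation is issued only after eligibility and consent have been logged. REDCap could serve if a randomization function is confirmed to be available.
2. **Envelopes outside IR.** The 24-hour research associates hold opaque, tamper-evident envelopes, opened strictly in number order after eligibility and consent are recorded, with a dated log. They suit this better than the trial office in section 12, which is not shown to be reachable at night. Because they also pre-screen, the seals and the log still matter.

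Under both routes the statistician prepares the sequence, and any block sizes are varied and withheld from IR. Section 6.4 should state the method and name, by role, who prepares, holds and releases each allocation.

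Cost: some set-up and a few minutes per patient before allocation. The sample size and the analysis do not change.

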7. INTERVENTIONS

The trial will compare two different devices: Coils (POD®, Penumbra, Alameda, CA, USA), and vascular plugs (Amplatzer™, Abbott Medical, Abbott Park, IL, USA).

7.1 POD® coils

Coils are FDA-approved endovascular occlusion devices that are longer than traditional coils and are deployed through a high-flow micro-catheter (Figure 1). Each type of coil comes in two varieties: 1) a helical coil sized to the vessel diameter that anchors the coil pack in the high-flow vessel and 2) a packing coil that is used to fill in the spaces within the helical coil. A typical pSAE using coils will involve the deployment of one helical coil followed by multiple packing coils until hemostasis is achieved.

7.2 Vascular plugs

Vascular plugs are FDA-approved endovascular occlusion devices that require an 0.035 inch system within the splenic artery for deployment (Figures 2 and 3). The Amplatzer™

IV vascular plug can be deployed through a traditional 5F diagnostic catheter. However, the largest Amplatzer™ IV vascular plug is only 8 mm in size, which may be too small for some splenic arteries. In these cases, a larger Amplatzer™ II vascular plug is needed although these vascular plugs require a larger system for deployment.

[figure not shown]

Figure 2. Picture of an
Amplatzer™ IV VP (from St. Jude
Medical)

[figure not shown]

Figure 3. Picture of an
Amplatzer™ II VP (from St. Jude
Medical)

7.3 Proximal Splenic Artery Embolization Procedure

An attending interventional radiologist will perform all SAE procedures using either moderate conscious sedation or general anesthesia depending on the patient's condition. The vascular access site is prepared and draped in standard sterile fashion.

Local anesthesia will be achieved with lidocaine. The right common femoral artery is the most commonly used vascular access for splenic artery embolization but the left common femoral artery may be used for certain patients. No radial artery access will be used. Regardless, the artery is accessed under direct sonographic guidance with a micro-puncture set. The micro-puncture set is then exchanged for a vascular sheath over a wire and attached to a heparinized saline flush. A celiac axis angiogram is then performed. The attending interventional radiologist will choose the diagnostic catheter based on his/her preference. The attending interventional radiologist will review the celiac angiogram to identify an appropriate landing zone in the mid-splenic artery distal to the origin of the dorsal pancreatic artery but proximal to the origin of the pancreaticomagna artery in order to preserve collateral flow to the spleen via the transverse pancreatic artery. The vessel's diameter at this location will be measured and recorded. For patients randomized to coil embolization, a high-flow micro-catheter is navigated to the location of embolization with the assistance of a micro-wire. The micro-wire-micro-catheter combination will be left to the discretion of the attending interventional radiologist. Once the micro-catheter is in place, a splenic angiogram will be performed. Coil embolization will then proceed per the manufacturer's instructions for use until satisfactory hemostasis is achieved. For patients randomized to vascular plug embolization, the appropriately-sized catheter or sheath is advanced to the location of embolization. The tools used to access the mid-splenic artery will vary depending on the operator's experience and patient anatomy. Once the catheter is in place, a splenic angiogram will be performed. Vascular plug embolization will then proceed per the manufacturer's instructions for use until satisfactory hemostasis is achieved. For both coil and vascular plug embolization, absence of flow at the level of the embolic agent in the mid-splenic artery will serve as the endpoint for satisfactory hemostasis. Regardless of the embolic used the interventional radiologist will perform intermittent angiograms (one per minute) to determine if stasis has been achieved. The time to hemostasis will be recorded. If hemostasis is not achieved after 15 minutes, then a secondary embolic can be employed. If a secondary embolic agent such as particles or gelfoam is needed for patients in either group, this will be recorded. All potential secondary embolic agents are FDA-approved devices and commercially available. Additionally, if the operator is unable to navigate into the mid-splenic artery with the necessary tools to perform the

required embolization, this will also be recorded. In this circumstance, the procedure will be recorded as a technical failure and the operator will then proceed to treat the patient as he/she deems appropriate. Catheters and wires will be removed after hemostasis is obtained in the mid-splenic artery. As is standard at our institution, the arteriotomy will be closed with a FDA-approved, commercially available vascular closure device, if possible. If the patient isn't a candidate for a vascular closure device, then hemostasis at the arteriotomy will be obtained with manual pressure, as is standard at our institution.

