and larger than traditional coils, namely POD® coils (Penumbra, Alameda, CA, USA). Using these larger coils can decrease the number needed to obtain hemostasis. These coils come in two varieties: 1) a helical coil sized to the vessel diameter that anchors the coil pack in the high-flow vessel thereby reducing the risk of distal migration and 2) a packing coil that is used to fill in the spaces within the helical coil. A typical pSAE using coils will involve the deployment of one helical coil followed by multiple packing coils until hemostasis is achieved.

Vascular plugs attempt to overcome the limitations of coils. For example, the deployment of a single vascular plug can typically provide hemostasis in the mid-splenic artery, theoretically reducing procedural time, contrast load, and radiation exposure. Despite this, vascular plugs are usually less familiar devices to endovascular specialists. Another drawback of vascular plugs is that they cannot be deployed through a standard micro-catheter but rather require the advancement of a larger, stiffer 0.035 inch system into the mid-splenic artery. This may limit their use in very tortuous splenic arteries. Vascular plugs reaching up to 8mm in size (Amplatzer™ IV, Abbott Medical, Abbott Park, IL, USA) can be deployed through a standard 5F diagnostic catheter. Larger vascular plugs (Amplatzer™ II) require at least a larger 6F guiding catheter.

Currently, the selection of embolic agent for pSAE is primarily based on operator experience and preference. The efficacy, technical success, and cost of using coils compared to vascular plugs has been evaluated in such conditions as pelvic congestion syndrome [10], yet, to the best of our knowledge, these embolic agents have never been compared for their use in pSAE, much less in a randomized, prospective fashion. We anticipate this pilot trial to demonstrate the feasibility of a larger study and provide sufficient information to identify appropriate primary endpoints. The innovation of this proposal is strengthened by the inclusion of over-reads of pre-procedural CT scans, which will allow accurate grading of splenic injury and information regarding associated vascular injury to the spleen. If found, significant differences between our study groups in either clinical outcomes, technical parameters, or cost would have an immediate impact on how we care for trauma patients both locally and nationally.

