8. OUTCOMES

Aim 1: Demonstrate feasibility by meeting enrollment and follow-up goals.

Objective 1a: Enroll at least 50% of eligible patients (50 patients total; 25 patients per arm)

Objective 1b: Obtain follow-up in at least 80% of enrolled patients

Aim 2: Assess for similarities and differences between the groups regarding clinical outcomes.

Objective 2a: Compare clinical outcomes of pSAE using coils versus vascular plugs (splenic salvage, immediate/delayed complications, patient length of stay, and post-embolization transfusion requirements)

Objective 2b: Compare technical outcomes of pSAE using coils versus vascular plugs (technical success (defined as the ability to access and embolize the mid-splenic artery), intra-procedural complications, necessity of a secondary embolic to obtain satisfactory hemostasis, and intra-procedural radiation doses)

Objective 2c: Conduct cost analysis of using coils versus vascular plugs (room time, equipment such as catheters, wires, and sheaths, and the cost of the embolic agent itself)

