- c) Signs of accompanying vascular injury such as pseudoaneurysm, extravasation, arterio-venous fistula, or hemoperitoneum
- d) Presence or absence of other intra-abdominal or extra-abdominal trauma

The following data points will be collected while the patient is admitted after the embolization procedure:

- a) Amount of blood products required

- b) Length of stay (ICU, floor, and total)
- c) Delayed complications (Abscess, bleeding, infarction, acute kidney injury)
- d) Secondary splenectomy (i.e. splenectomy needed after embolization)

The following data points will be collected at the 30 day follow up:

- a) Delayed complications (Abscess, bleeding, infarction, acute kidney injury)
- b) Secondary splenectomy

...

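### The Objective 2b dose comparison rests on one undivided figure, although required checks scale with time to hemostasis; a few added eCRF fields would make it interpretable

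*Combined protocol and SAP*

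**What the plan says.** Section 7.3 applies a single checking rule: "Regardless of the embolic used the interventional radiologist will perform intermittent angiograms (one per minute) to determine if stasis has been achieved". The endpoint that ends the checking is also common to both arms: "absence of flow at the level of the embolic agent in the mid-splenic artery will serve as the endpoint for satisfactory hemostasis". The section then adds: "The time to hemostasis will be recorded". It does not say when that clock starts. The next sentence reads: "If hemostasis is not achieved after 15 minutes, then a secondary embolic can be employed".

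Section 8 lists among the Objective 2b technical outcomes "necessity of a secondary embolic to obtain satisfactory hemostasis, and intra-procedural radiation doses". Section 3 expects the arms to differ. It says several coils may be needed, which may raise contrast use, procedural time and radiation. Of a single plug it says "theoretically reducing procedural time, contrast load, and radiation exposure".

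Section 9 introduces its variables with "A full list of variables to be collected is shown below". For the embolization procedure the list has one item for duration, one for radiation dose and one for contrast type and volume. It contains no time to hemostasis, no number of angiograms, no intermediate dose reading, and no height or weight. Section 11 compares continuous variables by Student's t-test and states no adjustment.

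**The concern.** Under section 7.3 the number of checking runs is close to the number of minutes until stasis. A patient who reaches stasis slowly is imaged more often, and that imaging adds to the dose compared under Objective 2b.

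The recorded total adds together three things: access and celiac angiography, which section 7.3 describes once for both arms; navigation and device delivery, which differ by arm; and the required checks. With one total per patient, a reader of the pilot could not tell which part produced a difference, or which part hid one. Differences in body size add further scatter that the planned test cannot remove, because the covariate is not collected.

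The stake is Aim 2, which is meant to identify endpoints for a larger trial. A dose difference that cannot be traced to its source is a weak basis for choosing or rejecting radiation as an endpoint. Most of the missing items are readings from the procedure and may not be recoverable afterwards unless they are logged at the time.

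**Working it through.** **Inputs from the documents.** One check per minute in both arms, and a secondary embolic permitted after 15 minutes (section 7.3). About 100 procedures a year, a 50% target, 25 per arm (section 10). Unadjusted t-test, threshold 0.05 (section 11), taken here as two-sided.

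**Step 1, the plan's own figure.** 0.50 × 100 = 50, or 25 per arm. It reproduces. The plan gives no power, SD, dose per run or expected time to hemostasis, so no stated number is in dispute.

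**Step 2, runs per patient.** Runs ≈ 1 per minute × T, where T is minutes to hemostasis. T = 1 gives about 1 run and T = 15 gives about 15, so two patients can differ by 14 runs before the 15-minute point. That point is not a cap, because a secondary embolic is allowed there, not required.

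**Step 3, arm difference due to checks.** Difference = dose per run × (mean T, coils − mean T, plugs). It is zero when the means are equal, and its sign follows whichever device is slower. For illustration, assume one run costs 1%, 3% or 5% of the dose from the rest of the procedure:

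| Difference in mean T | 1% per run | 3% per run | 5% per run |
|---|---|---|---|
| 0 min | 0% | 0% | 0% |
| 5 min | 5% | 15% | 25% |
| 14 min | 14% | 42% | 70% |

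**Step 4, set against the pilot's precision.** The difference detectable with 80% power at 25 per arm is (1.960 + 0.842) × √(2/25) = 0.79 SD. With an assumed dose SD of 40% to 60% of the same base dose, that is 0.792 × 40% = 32% to 0.792 × 60% = 48%. The checks' contribution could therefore be negligible or could exceed what the pilot can detect, depending on values that the documents do not give.

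**Step 5, what the listed data can separate.**

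| Needed | Section 7.3 | Section 9 list |
|---|---|---|
| Time to hemostasis | To be recorded; start undefined | Absent |
| Number of checking runs | Rule only | Absent |
| Dose and contrast before and after landing-zone selection | Not mentioned | One total each |
| Height and weight | Not mentioned | Absent |

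If section 7.3 is followed, time to hemostasis approximates the run count. If the eCRF is built from section 9, it is lost.

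**Step 6, value of a body-size covariate.** For correlation r with log dose, the gain is 1/(1 − r²). With r = 0.4, 0.5 and 0.6 (assumed) this is 1/0.84 = 1.19, 1/0.75 = 1.33 and 1/0.64 = 1.56, or 19% to 56% more patients for this outcome. On the log-dose scale, the detectable difference falls from 0.79 SD to 0.792 × √0.84 = 0.73 SD at r = 0.4, and to 0.792 × 0.80 = 0.63 SD at r = 0.6.

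**The case against.** The strongest reply is that the rule is identical in both arms and ends at one common endpoint. With equal stasis times it adds equal dose. With unequal times, slower occlusion is a property of the device, and the extra dose is a consequence of using it. A fixed interval also standardizes imaging across operators who know which device they are using. All of this stands. A reader might infer that the schedule manufactures a radiation difference or biases the comparison. The documents do not support that, because the rule only scales a real difference. They also do not state the usual checking frequency, so the protocol's share of the dose is unknown, as is its direction relative to ordinary practice.

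Four further inferences are tempting and should not be drawn.

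- *Only whole-procedure totals are kept.* Section 7.3 says time to hemostasis is recorded. The defect is that section 9 does not list it.
- *The checks lengthen the procedure.* The interval until stasis passes whether or not it is imaged.
- *The totals include other vessels treated in the same session.* No section describes such treatment. The related CT item, "Presence or absence of other intra-abdominal or extra-abdominal trauma", concerns injuries seen, not treated.
- *Check-run dose should be subtracted.* Run count and two cumulative readings do not isolate it without assuming a dose per run, since the same interval holds navigation, the splenic angiogram and deployment. Subtraction would also remove part of a device effect that arises after randomization.

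Body size is balanced in expectation by randomization, so omitting it costs precision and does not bias the comparison. The documents do not say how strongly it drives dose. That limits the claim to a possible gain in efficiency.

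**Conclusion.** The point holds as a data-collection and interpretation gap. The documents establish three things: checking runs scale with time to hemostasis; sections 7.3 and 9 disagree on whether that time is captured; and the Objective 2b dose comparison uses one undivided, unadjusted total.

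The size of the consequence cannot be derived from the documents. The dose shifts and the 19% to 56% gain both rest on assumed inputs: dose per run, difference in stasis time, dose SD, and correlation with body size. Restricting dose to the interval from landing zone to hemostasis gains precision only if the earlier dose is not strongly negatively related to the later dose, which is also an assumption.

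Severity is low. Radiation is one of many secondary outcomes in a pilot whose primary outcome is feasibility, and the plan does not state that a radiation effect or SD will feed a later sample-size calculation.

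**What to change.** Leave the clinical procedure unchanged. Reconcile sections 7.3 and 9, and add these fields to the eCRF:

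1. Time to hemostasis, with a defined start that applies to both arms.
2. Number of checking angiograms.
3. Cumulative radiation dose and contrast volume at landing-zone selection and again at hemostasis, or at the end of the attempt for technical failures.
4. Height and weight.

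In section 11, state that whole-procedure dose, adjusted for body size, is the intention-to-treat comparison for Objective 2b. The log scale would suit this, since the gain above is stated for log dose. Add landing-zone-to-hemostasis dose as a second, device-specific comparison. Report run count and time to hemostasis descriptively by arm, and do not subtract check-run dose.

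The cost is a few eCRF fields, a short addition to the analysis section, and slightly more logging by room staff. The change has to be made prospectively.
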